2 ABBREVIATIONS

AAO	American Academy of Ophthalmology
AC	anterior chamber
ADE	adverse device effect
AE	adverse event
ALT	argon laser trabeculoplasty
ANOVA	analysis of variance
BCVA	best corrected visual acuity
CAI	carbonic anhydrase inhibitor
CCT	central corneal thickness
C:D	cup-to-disc ratio
CF	count fingers
CI	confidence interval
D	diopter
dB	decibel
DSEK	Descemet stripping endothelial keratoplasty
ECD	endothelial cell density
ECL	endothelial cell loss
eCRF	electronic case report form
ETDRS	Early Treatment Diabetic Retinopathy Study
HM	hand motion
HVF	Humphrey visual field (perimeter)
ICD	informed consent document
ICF	informed consent form
IDE	investigational device exemption
IOL	intraocular lens
IOP	intraocular pressure
IRB	institutional review board
KM	Kaplan-Meier
LogMAR	logarithm of minimal angle of resolution
LP	light perception
LTF	lost to follow-up
MD	mean deviation
MGD	meibomian gland disease
MIGS	minimally invasive glaucoma surgery
NLP	no light perception
OAG	open-angle glaucoma
OCT	optical coherence testing
OD	right eye
OS	left eye
OU	both eyes
OVD	ophthalmic viscosurgical device

**CYPASS® MICRO-STENT
PROTOCOL TMI-09-01-E VERSION G**

PAS	peripheral anterior synechiae
PCO	posterior capsular opacification
PDR	proliferative diabetic retinopathy
POAG	primary open-angle glaucoma
SAE	serious adverse event
SAP	statistical analysis plan
SLT	selective laser trabeculoplasty
SOP	standard operating procedure
TFBUT	tear film break-up time
TLR	total letters read
UADE	unanticipated adverse device effect
VA	visual acuity
VF	visual field

**CYPASS® MICRO-STENT
PROTOCOL TMI-09-01-E VERSION G**

3 STUDY SYNOPSIS

3.1 Study Objective

The purpose of this research study is to evaluate the long-term safety of the CyPass Micro-Stent in subjects who have completed Study Protocol TMI-09-01.

3.2 Study Population

The study population will consist of up to 480 eyes of 480 subjects who completed 24 month follow-up in study Protocol TMI-09-01 and meet study eligibility criteria.

3.3 Study Design

This is a multicenter, observational study with no planned interventions. Both prospective and retrospective data on participating subjects may be collected in the study.

3.4 Study Outcomes

3.4.1 Primary Outcome - Safety

- Rate of occurrence of sight-threatening AEs

3.4.2 Secondary Outcomes - Safety

- Best Corrected Visual Acuity (BCVA)
- Rate of occurrence of ocular adverse events (AE)
- Slit lamp, gonioscopy and fundus findings
- Visual field mean deviation (MD)
- Central corneal thickness
- Central corneal endothelial cell density (ECD)
- Rate of occurrence of CyPass movement, defined as a change by at least 1 in the number of CyPass rings visible (e.g., from 0 rings to 1 ring or from 3 rings to 2 rings) that does not result in clinical sequelae (e.g., secondary surgical intervention to modify device position, corneal endothelial touch by device, corneal edema leading to loss of BCVA > 2 lines at the last postoperative visit in comparison with preoperative BCVA, progressive ECL, erosion of device through sclera, or device obstruction requiring secondary surgical intervention), and that is not attributable to:
 - variations in gonioscopic viewing angle or illumination,
 - changes in angle anatomy due to concomitant findings such as resolution of hyphema,
 - changes in anterior chamber depth, or
 - development of focal peripheral anterior synechiae.

**CYPASS® MICRO-STENT
PROTOCOL TMI-09-01-E VERSION G**

3.4.3 Secondary Outcomes – Effectiveness

- Mean change in intraocular pressure (IOP)
- Proportion of subjects who are not using ocular hypotensive medication with $\geq 20\%$ reduction in IOP from baseline in the COMPASS Trial
- Proportion of subjects who are not using ocular hypotensive medication with IOP ≥ 6 mmHg and ≤ 18 mmHg

3.5 Schedule of Visits

Subjects are to be evaluated at 36 months, 48 months and 60 months post-randomization in study protocol TMI-09-01 (See [APPENDIX 1](#) – Schedule of Events and Procedures).

**CYPASS® MICRO-STENT
PROTOCOL TMI-09-01-E VERSION G**

4 INTRODUCTION AND RATIONALE

4.1 The CyPass Micro-Stent

As shown in Figure 1 below, the CyPass Micro-Stent is a polyimide tube with a fenestrated through-lumen. The length of the CyPass device is 0.250" (6.35 mm). The device has a 0.012" (0.30 mm) inner diameter and 0.017" (0.43 mm) outer diameter. The CyPass Micro-Stent, when implanted as directed, is designed to allow outflow of aqueous fluid from the AC of the eye (where the device proximal end resides) through and around the distal end of the tube into the supraciliary and suprachoroidal spaces.

**Figure 1
CyPass Micro-Stent**

4.2 Protocol Background and Rationale

Protocol TMI-09-01, also known as the COMPASS Trial, was a prospective, randomized, comparative multicenter study to assess the safety and effectiveness of the CyPass Micro-Stent in subjects with primary open angle glaucoma who were undergoing cataract surgery. In the study, a total of 505 subjects were randomized to one of two treatment groups, as follows: The CyPass group underwent cataract surgery and received the CyPass Micro-Stent, while the Control group underwent cataract surgery alone. All subjects randomized were followed for 2 years postoperatively.

The study was performed in 2 phases. During the initial phase, 75 subjects were randomized. After FDA review of 3 month or longer postoperative data on these subjects, approval was granted for enrollment and randomization of the remaining 430 subjects in the study expanded phase. Enrollment in the initial study phase began in September 2009 and ended in August 2010. Enrollment in the expanded phase of the study began in July 2011 and the last study subject was randomized in March 2013.

**CYPASS® MICRO-STENT
PROTOCOL TMI-09-01-E VERSION G**

Subjects enrolled in the COMPASS Trial were examined at 2 preoperative visits to confirm eligibility for study participation. The first visit (Screening Visit) involved a comprehensive ophthalmic examination. Subjects qualifying after completion of the Screening Visit were required to discontinue use of ocular hypotensive medication, or “washout”, for a pre-established period to remove the medication from their system. After washout, subjects returned for a Baseline Visit during which they were re-evaluated and additional baseline data was collected to confirm continued eligibility. Subjects who qualified after the Baseline Visit were scheduled for cataract surgery. After completion of uncomplicated cataract surgery, subjects were randomized intraoperatively to either the CyPass group or the Control group. Subjects were asked to return for examination at postoperative Day 1, Week 1, Month 1, Month 3, Month 6, Month 12, Month 18 and Month 24.

Study protocol TMI-09-01-E, the COMPASS Extension Trial, is designed to collect safety data beyond 24 months postoperatively for subjects who completed study protocol TMI-09-01. [REDACTED]
[REDACTED] Study enrollment was initiated April 2016.

**CYPASS® MICRO-STENT
PROTOCOL TMI-09-01-E VERSION G**

5 STUDY OBJECTIVES

The purpose of this research study is to evaluate the long-term safety of the CyPass Micro-Stent in subjects who completed Study Protocol TMI-09-01.

5.1 Study Outcomes

5.1.1 Primary Outcome – Safety

- Rate of occurrence of sight-threatening AEs

5.1.2 Secondary Outcomes - Safety

- Best Corrected Visual Acuity (BCVA)
- Rate of occurrence of ocular adverse events (AE)
- Slit lamp, gonioscopy and fundus findings
- Visual field mean deviation (MD)
- Central corneal thickness
- Central corneal endothelial cell density (ECD)
- Rate of occurrence of CyPass movement, defined as a change by at least 1 in the number of CyPass rings visible (e.g., from 0 rings to 1 ring or from 3 rings to 2 rings) that does not result in clinical sequelae (e.g., secondary surgical intervention to modify device position, corneal endothelial touch by device, corneal edema leading to loss of BCVA > 2 lines at the last postoperative visit in comparison with preoperative BCVA, progressive ECL, erosion of device through sclera, or device obstruction requiring secondary surgical intervention), and that is not attributable to:
 - variations in gonioscopic viewing angle or illumination,
 - changes in angle anatomy due to concomitant findings such as resolution of hyphema,
 - changes in anterior chamber depth, or
 - development of focal peripheral anterior synechiae.

5.1.3 Secondary Outcomes – Effectiveness

- Mean change in intraocular pressure (IOP)
- Proportion of subjects who are not using ocular hypotensive medication with $\geq 20\%$ reduction in IOP from baseline in the COMPASS Trial
- Proportion of subjects who are not using ocular hypotensive medication with IOP ≥ 6 mmHg and ≤ 18 mmHg

**CYPASS® MICRO-STENT
PROTOCOL TMI-09-01-E VERSION G**

6 STUDY DESIGN

Study Protocol TMI-09-01-E is a multicenter observational study. Up to 480 subjects randomized in the COMPASS Trial at up to 24 investigational sites may participate. Study data through 5 years post-randomization in the COMPASS Trial will be collected for subjects who consent to participate.

7 STUDY POPULATION

7.1 Subject Inclusion Criteria

To be included in the study, individuals must meet each eligibility criterion presented as follows:

1. Participated in, and completed, Study Protocol TMI-09-01.
2. Is able to understand study requirements and willing to follow study instructions
3. Is willing to return for required study follow-up visits.

7.2 Subject Exclusion Criteria

The presence of any of the following characteristics will exclude individuals from study participation:

1. Systemic disease that, in the opinion of the Investigator, would put the subject's health at risk and/or prevent completion of required study visits.
2. Early termination from Study Protocol TMI-09-01.

**CYPASS® MICRO-STENT
PROTOCOL TMI-09-01-E VERSION G**

8 STUDY PROCEDURES

8.1 Subject Entry

Participants who completed Protocol TMI-09-01 (the COMPASS Trial) will be asked to enroll in the study. The investigator or designee will explain the study purpose, procedures and responsibilities to the potential participant and provide sufficient opportunity to ask questions, while allowing adequate time for consideration of the information provided. Upon participant confirmation of interest, written informed consent will be obtained and the subject will be enrolled in the study. One copy of the informed consent document (ICD) will be retained with the subject's medical records and one copy will be provided to the subject.

8.2 Study Visits

All subjects enrolled will return for defined follow-up visits through 60 months post-randomization in the COMPASS Trial. The number of scheduled study visits required will be dependent on the date of subject randomization in the COMPASS Trial. Data collected from each study visit will be recorded on an electronic Case Report Form (eCRF).

8.2.1 36 Month Postoperative Visit

This visit will occur at postoperative day 1095 ± 90 days. The following information will be captured for the study eye at this visit:

- Manifest refraction and ETDRS BCVA
- Slit lamp biomicroscopy
- Goldmann tonometry
- Dilated fundus examination and C:D ratio assessment
- Visual field mean deviation
- Gonioscopy examination (CyPass-implanted eyes only)
- Central corneal pachymetry
- Specular microscopy
- Ocular hypotensive medications
- AE assessment
- Subject Symptom Questionnaire

In the event a subject is enrolled who is more than 36 months postoperative, retrospective data for the 36-month follow-up period, if available, may be collected from review of the subject's medical chart.

**CYPASS® MICRO-STENT
PROTOCOL TMI-09-01-E VERSION G**

8.2.2 48 Month Postoperative Visit

This visit will occur at postoperative day 1460 ± 90 days. The following information will be captured for the study eye at this visit:

- Manifest refraction and ETDRS BCVA
- Slit lamp biomicroscopy
- Goldmann tonometry
- Dilated fundus examination and C:D ratio assessment
- Visual field mean deviation
- Gonioscopy examination (CyPass- implanted eyes only)
- Central corneal pachymetry
- Specular microscopy
- Ocular hypotensive medications
- AE assessment
- Subject Symptom Questionnaire

In the event a subject is enrolled who is more than 48 months postoperative, retrospective data for the 48-month follow-up period, if available, may be collected from review of the subject's medical chart.

8.2.3 60 Month Postoperative Visit

This visit must occur at postoperative day 1825 ± 90 days. The following information will be captured for the study eye at this visit:

- Manifest refraction and ETDRS BCVA
- Slit lamp biomicroscopy
- Goldmann tonometry
- Dilated fundus examination and C:D ratio assessment
- Visual field mean deviation
- Gonioscopy examination (CyPass-implanted eyes only)
- Central corneal pachymetry
- Specular microscopy
- Ocular hypotensive medications
- AE assessment
- Subject Symptom Questionnaire

In the event a subject is enrolled who is more than 60 months postoperative, retrospective data for the 60-month follow-up period, if available, may be collected from review of the subject's medical chart.

**CYPASS® MICRO-STENT
PROTOCOL TMI-09-01-E VERSION G**

The examinations required at each study visit are outlined and summarized in [APPENDIX 1](#) (Schedule of Events and Procedures) and a description of examination methodology is provided in [APPENDIX 2](#) (Examination Procedures, Tests, Equipment and Techniques).

8.3 Unscheduled Visits

Unscheduled visits are clinic visits not specified in the protocol when the subject returns for examination due to a complaint regarding the study eye or a surgical procedure performed on the study eye. No specific testing is required at unscheduled visits; rather, the investigator and/or qualified investigational staff will perform the examinations or procedures necessary to evaluate the subject at these visits. Clinical data from unscheduled visits will be recorded on the relevant eCRF.

8.4 Subject Disposition

8.4.1 Discontinued Subjects

Subjects who exit the study prior to completion are considered to be “discontinued”. Subjects may be discontinued due to:

- Onset or progression of systemic disease that, in the opinion of the investigator, would put the subject’s health at risk or compromise the subject’s ability to return for necessary follow-up visits, or
- Administrative reasons (e.g., voluntary withdrawal or loss to follow-up)

The sponsor should be promptly notified of subject discontinuation and the relevant eCRF should be completed for this subject.

If a subject does not return for a scheduled study visit, the investigational site will make a minimum of 3 documented attempts via telephone, email, or regular mail to contact the subject. If the subject does not reply to any of these attempts, the site will send a letter to the subject using certified mail, with a request for notification of receipt. If a subject continues to be non-responsive to these follow-up attempts, the subject will be considered to be lost to follow-up.

8.4.2 Completed Subjects

Completed subjects are those who are not discontinued from the study prior to completion of required scheduled visits.

**CYPASS® MICRO-STENT
PROTOCOL TMI-09-01-E VERSION G**

9 STATISTICAL METHODS

The objective of this study is to collect long-term safety data regarding the CyPass Micro-Stent in subjects who completed the COMPASS Trial. The primary outcome is the occurrence of sight-threatening AEs. Other study outcomes include the rate of occurrence of ocular AEs in the study eye, BCVA, slit lamp, gonioscopy and fundus examination findings, central corneal thickness, central corneal ECD. Study outcomes will be analyzed as follows.

9.1 Sight Threatening Ocular Adverse Events

Sight-threatening AEs include, but are not limited to, BCVA loss of ≥ 3 lines, endophthalmitis, corneal decompensation, severe retinal detachment, severe choroidal hemorrhage, severe choroidal detachment and aqueous misdirection. A non-parametric time to event Kaplan-Meier (K-M) analysis for the sight-threatening AE rate at 5 years will be provided by treatment group. This method accounts for all information that discontinued patients contribute to the rate of the primary safety event up to the point at which that patient discontinues (i.e., is censored). The cumulative Kaplan-Meier probability that a subject experienced a sight-threatening AE will be completed for each treatment group. To aid in the interpretation of the results, the annualized rates for each year and over the five (5) year period will be calculated.

9.2 Ocular Adverse Events

The number of subjects reporting at least 1 AE of a given type will be summarized. AEs not listed that occur during the study will be added to the summary of AEs. Each AE will be summarized by incidence, percentage and 95% confidence interval.

9.3 Central Corneal Pachymetry

Central corneal pachymetry data collected at baseline, 12 month and 24 month postoperative visits in Protocol TMI-09-01 and collected in this protocol will be summarized with N, mean, standard deviation, minima, median, and maxima. A 95% confidence interval will be provided for the change and percentage change from baseline. Change between 2 consecutive visits will also be summarized.

9.4 Central Corneal Endothelial Cell Density

Endothelial cell density (ECD) data collected at baseline, 3 month, 6 month, 12 month and 24 month postoperative visits in Protocol TMI-09-01 and in this protocol will be summarized with N, mean, standard deviation, minima, median, and maxima for each treatment arm. A 95% confidence interval will be provided for the change and percentage change in ECD from baseline. The change between 2 consecutive visits will also be summarized.

**CYPASS® MICRO-STENT
PROTOCOL TMI-09-01-E VERSION G**

9.5 Best Corrected Visual Acuity

Best Corrected Visual Acuity (BCVA) data collected at the subject baseline, 12 month and 24 month postoperative visits in Protocol TMI-09-01 and in this protocol will be summarized as counts and percentages with 95% confidence intervals for subjects who have BCVA 20/20 or better, 20/25 or better, 20/32 or better, 20/40 or better and worse than 20/40. Also, shift tables from baseline will be presented with counts, percentages, and 95% confidence intervals.

9.6 Slit Lamp, Gonioscopy and Fundus Exam Findings

Slit lamp, gonioscopy, and fundus examination findings at scheduled follow-up visits will be tabulated such that the number and percentage of subjects in each category and 95% confidence intervals for the percentages will be summarized by scheduled follow-up visit.

9.7 Visual Field Loss Mean Deviation

The visual field mean deviation (MD) testing data collected at baseline, 3 month, 6 month, 12 month and 24 month postoperative visits in Protocol TMI-09-01 and in this protocol will be summarized with N, mean, standard deviation, minima, median, and maxima. A 95% confidence interval will be provided for the change and percentage change from baseline.

9.8 Intraocular Pressure

The N, mean, standard deviation, minima, median, and maxima for change in IOP will be presented for each study visit, along with a 95% confidence interval on the mean change. The number and proportion of subjects who are not using ocular hypotensive medication with $\geq 20\%$ reduction in IOP from baseline in the COMPASS Trial will also be presented at each study visit, along with a 95% confidence interval. Finally, the number and proportion of subjects who are not using ocular hypotensive medication with IOP ≥ 6 mmHg and ≤ 18 mmHg will be presented at each study visit, along with a 95% confidence interval.

**CYPASS® MICRO-STENT
PROTOCOL TMI-09-01-E VERSION G**

10 ADVERSE EVENTS

All ocular AEs occurring in the study eye must be reported on the relevant eCRF. Adverse events will be categorized by degree of harm to the subject (mild, moderate, or severe) and the relationship to the CyPass Micro-Stent. Since there are no aspects of the study that can affect both eyes, only serious adverse events observed in the fellow eye must be reported. Serious non-ocular AEs will also be captured on the relevant eCRF throughout the course of the study.

Ocular conditions or diseases present at the time of study enrollment in Study Protocol TMI-09-01 will be considered as “baseline”. Changes in a chronic condition or disease that are consistent with natural disease progression are not considered to be AEs. The status of AEs that were “ongoing” at subject exit from Study Protocol TMI-09-01 will be evaluated at the time of enrollment in this study. Events that remain ongoing and that meet the AE definitions for this protocol will be documented as AEs in this study

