10.1 Ocular Adverse Events

Ocular AEs that might reasonably be expected to occur include, but are not limited to, the following:

- BCVA loss of 2 lines (10 letters) or more on the ETDRS chart in comparison with the best BCVA reported in Study Protocol TMI-09-01
- Any 2-point worsening in slit lamp examination findings (other than cells and flare) to “severe or “very severe”, which is not associated with a pre-existing condition
- Chronic anterior uveitis, defined as inflammation of Grade 1+ or worse persisting for more than 3 months post-operatively or that recurs less than 3 months after discontinuation of anti-inflammatory treatment
- Endophthalmitis
- Presence of flat anterior chamber requiring anterior chamber reformation
- Presence of a shallow chamber with iridocorneal apposition without lens/cornea touch
- Corneal edema
- Corneal decompensation
- Corneal opacification
- Hyphema, which is > 2 mm in size
- Retinal detachment
- Proliferative vitreoretinopathy
- Other retinal complications (e.g., dialysis, flap tears)
- Increase in C:D ratio of ≥ 0.3 units in comparison with the 24-month C:D ratio reported in Study Protocol TMI-09-01
- A confirmed worsening in visual field mean deviation (MD) of ≥ 2.5 dB compared to the 24-month visual field MD determined in Study Protocol TMI-09-01
- Suprachoroidal hemorrhage
- Choroidal effusion requiring surgical drainage

**CYPASS® MICRO-STENT
PROTOCOL TMI-09-01-E VERSION G**

- Choroidal effusion or detachment with at least a partially hemorrhagic component that obstructs vision or causes pain (including both peripheral and “kissing” choroidal detachments) lasting longer than 30 days
- Hypotonic maculopathy
- Macular edema (including cystoid macular edema and diabetic macular edema)
- Choroidal folds
- Other maculopathy
- Clinically significant hypotony, which is defined as IOP < 6 mmHg that results in maculopathy; flat anterior chamber requiring reformation; corneal folds; onset or worsening of with-the-rule astigmatism by ≥ 1 Diopter or rotation of against-the-rule to with-the-rule astigmatism by ≥ 1 Diopter; choroidal effusion requiring surgical drainage; suprachoroidal hemorrhage or BCVA loss of ≥ 2 lines
- Mean (or median) IOP ≥ 10 mmHg higher than the subject’s baseline mean unmedicated diurnal IOP reported in Protocol TMI-09-01
- CyPass device obstruction by iris, vitreous, lens, fibrous overgrowth, fibrin or blood
- CyPass device malfunction

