10.2 Sight-Threatening Ocular Adverse Events

Sight-threatening AEs include, but are not limited to endophthalmitis, corneal decompensation, BCVA loss ≥ 3 lines, severe retinal detachment, severe choroidal hemorrhage, severe choroidal detachment and aqueous misdirection.

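### The protocol excludes natural disease progression from AEs but lists BCVA loss, C:D increase and visual field worsening as AEs without saying which rule prevails; through 3-line BCVA loss this reaches the primary outcome.

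*Protocol*

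**What the plan says.** Protocol section 10 treats ocular disease present at enrolment in the parent COMPASS Trial as baseline and then gives a general rule: "Changes in a chronic condition or disease that are consistent with natural disease progression are not considered to be AEs". It gives no criterion for natural progression, names no assessor and makes no exception for any listed event. Section 4.2 describes the parent trial's population as "subjects with primary open angle glaucoma who were undergoing cataract surgery", so glaucoma is a baseline condition for every subject.

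Section 10.1 lists these among the expected ocular AEs:

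- For acuity: "BCVA loss of 2 lines (10 letters) or more on the ETDRS chart in comparison with the best BCVA reported in Study Protocol TMI-09-01"
- For the optic disc: "Increase in C:D ratio of ≥ 0.3 units in comparison with the 24-month C:D ratio reported in Study Protocol TMI-09-01"
- For the field test, with the Month 24 result as its reference: "A confirmed worsening in visual field mean deviation (MD) of ≥ 2.5 dB"

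Section 10.2 names "BCVA loss ≥ 3 lines" as a sight-threatening AE, and Protocol 9.1 and SAP 5.1 repeat it. The primary outcome is the rate of sight-threatening AEs, estimated by Kaplan-Meier at 5 years in each treatment group (SAP 5.1).

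**The concern.** The two rules can give opposite answers for the same eye. Field worsening and cup enlargement are changes that an investigator can readily attribute to glaucoma. A 3-line acuity loss can be attributed to glaucoma or to another chronic disease. Under the general rule in section 10 such a change is not an AE. Under the list in 10.1 or 10.2 it is.

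The study tests no hypotheses (SAP section 4), so descriptive event rates are its main product. If inclusion turns on a judgement about cause, rates can differ among up to 24 sites because the sites read the protocol differently. They can also differ between arms if knowledge of the implant influences that judgement. An event judged not to be an AE would also not be assessed for seriousness under 10.5.

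**Working it through.** The plan states no figure for this point, so there is none to reproduce. The check is a comparison of the texts, followed by an illustration.

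**1. Do the rules overlap?**

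| Event | Section 10 general rule | Sections 10.1 and 10.2 | Named primary component? |
|---|---|---|---|
| BCVA loss ≥ 2 lines | Not an AE if judged progression | AE, no cause qualifier | No |
| BCVA loss ≥ 3 lines | Same | Sight-threatening AE, no cause qualifier | Yes |
| C:D increase ≥ 0.3 from Month 24 | Same | AE, no cause qualifier | No |
| Confirmed MD worsening ≥ 2.5 dB from Month 24 | Same | AE, no cause qualifier | No |

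They overlap in every row, and no sentence sets precedence.

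**2. Does the assessor know the arm?** No section available in the public copy describes masking or adjudication. Gonioscopy is done only in CyPass eyes (Protocol 8.2 and Appendix 1), and each AE is rated for its relationship to the device (section 10). Knowledge of the arm is therefore likely, but it is an inference.

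**3. Do other SAP tables recover an excluded event?**

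- *BCVA.* SAP 5.5 gives shift tables from baseline, which SAP section 2 defines as the COMPASS Baseline Visit. That visit preceded cataract surgery (Protocol 4.2). Section 10.1 equates 2 lines with 10 letters, so 1 line is 5 letters and 3 lines are 15. If an eye gained g letters after surgery and then lost 15 from its best value, its change from baseline is g − 15. For g ≥ 15 the shift table shows no loss.
- *MD.* SAP 5.7 summarises means and changes, from baseline and from Month 24, by arm. It does not count eyes past 2.5 dB.
- *C:D.* SAP 5.6 tabulates fundus findings by category. It specifies no count of eyes past 0.3.

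**4. Illustration for the primary rate.** Let p be the true 5-year rate, s the share of events that are BCVA loss, and e the fraction of those set aside as progression. Ignoring censoring and counting one event per subject:

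recorded rate = p × (1 − s × e)

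All three inputs are assumptions: p = 5% in both arms (true ratio 1.0) and s = 30% or 60%, with e as shown.

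| e, CyPass / control | s | CyPass | Control | Ratio |
|---|---|---|---|---|
| 50% / 50% | 30% | 5% × 0.85 = 4.25% | 4.25% | 1.00 |
| 50% / 50% | 60% | 5% × 0.70 = 3.50% | 3.50% | 1.00 |
| 50% / 25% | 30% | 4.25% | 5% × 0.925 = 4.63% | 0.92 |
| 50% / 25% | 60% | 3.50% | 5% × 0.85 = 4.25% | 0.82 |
| 50% / 0% | 30% | 4.25% | 5.00% | 0.85 |
| 50% / 0% | 60% | 3.50% | 5.00% | 0.70 |

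The ratio does not depend on p, so it is the same at p = 2% or 10%. Exchanging the arms inverts it. Equal exclusion leaves the ratio at 1.0 but lowers both rates.

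**The case against.** The strongest reply is that the list is meant to prevail.

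- Three other items in 10.1 (slit lamp findings, chronic pain and the symptom questionnaire) carry their own exclusion for pre-existing conditions. The BCVA, C:D and MD items do not, which suggests that the drafters added a cause exclusion where they wanted one.
- Measuring C:D and MD change from Month 24 would have little purpose in a glaucoma population if the general rule removed these events.
- The list also includes diabetic macular edema, a complication of chronic disease.

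This is the better reading, and I would expect many sites to adopt it. It remains an inference. Section 10 does refer to events meeting the protocol's AE definitions, but only for events carried over from COMPASS.

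Other safeguards help in part. Serious events are reportable whatever their relationship to the device (10.5), and monitoring is meant to check AE reporting (section 11). Both apply only after something has been classed as an AE, and a monitor would need the same missing rule. The SAP's MD and BCVA summaries keep progression visible in the report but do not restore threshold events.

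A reader might go further and infer that nearly every field or disc change in these eyes counts as natural progression, which would leave the listed items empty. The documents do not support that: the thresholds may equally mark what exceeds expected progression.

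**Conclusion.** The conflict is real, is in the current text and should be resolved. It reaches the primary analysis by one named route, BCVA loss of 3 or more lines. C:D and MD affect the ocular AE rates. A reader might infer that all three feed the primary outcome; the sight-threatening list is open-ended, but only BCVA loss is named in it.

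Three further inferences are not supported:

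- *That sites dropped events, or that the CyPass rate is biased downward.* The text permits exclusion. It does not show that exclusion happened or in which direction.
- *That assessment is unmasked by design.* This rests on the CyPass-only gonioscopy and the device-relationship rating. No section says it.
- *That a definite share of eyes would cross the MD threshold.* This would need a progression rate and a variability that the documents do not give, and it would have to allow for the requirement that worsening be confirmed.

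The size of the effect cannot be derived from the documents. The ratios of 0.70 to 1.00 above follow wholly from the assumed values of s and e and show only what is possible.

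**What to change.** 1. **Reconcile sections 10 and 10.1.** State that the BCVA, C:D and MD items in 10.1 and the BCVA item in 10.2 are recorded as AEs whatever the suspected cause. Record attribution to progression in a separate field. Leave unchanged the slit lamp, chronic pain and questionnaire items. A blanket sentence covering all of 10.1 would contradict their own exclusions.
2. **Derive the primary BCVA event in the SAP.** Compute loss of 3 or more lines from total letters read at each visit, in both arms, against a stated reference. Protocol 9.1 and 10.2 and SAP 5.1 give none; the best COMPASS BCVA already used in 10.1 is one option. Because adding derived events changes how the endpoint is ascertained, report the Kaplan-Meier estimate that includes them alongside the estimate from reported AEs.
3. **Tabulate the other thresholds.** Count by arm the eyes crossing the C:D and MD thresholds from Month 24, and show unconfirmed MD crossings separately from confirmed ones.

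The cost is a short protocol clarification, one added field and a few extra tables, using examinations already scheduled. Recorded AE rates may rise.
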